With the implementation of protocol amendment 9 (Version 6.0), no further subjects were recruited. Subjects that started to a regimen with 3-months treatment courses should finish the treatment course as planned. Subjects that started to a regimen with treatment courses of 6 months duration should finish the first 3 months, if they are currently in the first 84 days of that treatment course, finish the second 3 months, if they are currently beyond day 84 of the treatment course. Thus, with the implementation of protocol amendment 9 and the originally foreseen study design outlined in [Figure 3-1](#) is not applicable anymore for vilaprisan groups. Subjects in treatment group B can continue the study course following the current valid version of the protocol.

With the implementation of Protocol Amendment 10 (version 7.0), this study design as outlined in [Figure 3-1](#) is no longer valid. No subjects will receive further study drug treatment. All subjects who were randomized and started treatment before the temporary pause were asked to have a comprehensive safety evaluation (with particular focus on endometrial, adrenal and skin safety) performed. This also applies to subjects who have completed or discontinued the study before or during the temporary pause, provided they have taken at least one dose of study medication.

Likewise, subjects randomized to treatment group B who are still in the study will be asked to undergo these procedures.

At the time study treatment was terminated, no subjects in subgroup 2 had reached the second year of treatment. Therefore, the statistical analysis will include patients from both subgroups without any distinction.

Figure 3-1 Design overview

Subgroup 1 (about 1 year of treatment)

A1	SCR up to 90 days	RND	12 wk trt	B	12 wk trt	B	12 wk trt	B	12 wk trt	24 wk FUP
A2	SCR up to 90 days	RND	24 wk trt		B	B	24 wk trt		24 wk FUP	
A3	SCR up to 90 days	RND	12 wk trt	B	B	12 wk trt	B	B	12 wk trt	24 wk FUP
B	SCR up to 90 days	RND	Symptomatic nonhormonal medical treatment as determined by the investigators and/or watch and wait						24 wk FUP	

Subgroup 2 (about 2 years of treatment)

A1	SCR up to 90 days	RND	12 wk trt	B	12 wk trt	B	12 wk trt	B	12 wk trt	B	12 wk trt	B	12 wk trt	B	12 wk trt	B	12 wk trt	12 wk FUP
A2	SCR up to 90 days	RND	24 wk trt		B	B	24 wk trt		B	B	24 wk trt		B	B	24 wk trt		12 wk FUP	
A3	SCR up to 90 days	RND	12 wk trt	B	B	12 wk trt	B	B	12 wk trt	B	B	12 wk trt	B	B	12 wk trt	B	B	12 wk FUP

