4.5 Data Rules

Reference Start/End dates

For vilaprisan (VPR), the reference start and end dates refer to the first and last study drug intake and will be identified based on the eCRF entry (EXCATN=1). For subjects with study drug exposure unknown, the randomization date will be used as the reference start date, and the end date of last scheduled/ unscheduled visit according SV (Subject Visits dataset) will be used as the reference end date.

Missing or partially missing eCRF end dates will be replaced by the date of the last study drug intake according to the diary. In case there is no study drug intake recorded in the diary, the date of the last available visit/contact will be used, which is the maximum of the end date of last scheduled/ unscheduled visit according SV (Subject Visits dataset), and the “last visit” as collected on the eCRF page for Disposition dataset. For subjects randomized to VPR who did not take any treatment (FAS not SAF), the last available visit date will be used as the reference start date and the reference end date.

For treatment group B the reference start date is defined by the randomization date. The reference end date is defined by the start date of the End of Treatment (EoT) visit (unscheduled EoT visits not considered). Missing EoT visit dates will be replaced by the end date of the last available visit before the safety closeout visit (refer to Table 4-1). If a subject in treatment group B has no safety

closeout visit, missing EoT visit dates will be replaced by the date of last scheduled/ unscheduled visit according SV (Subject Visits dataset).

For both VPR and treatment group B, the reference end date after the missing replacement with the rules defined above should be no earlier than the reference start date. Otherwise, the reference end date will finally be replaced by the reference start date.

For any analysis, if date of first study drug exposure/ date of last study drug exposure is used, the reference start/end date for treatment group B defined as above will be used for the analysis in treatment group B, if applicable.

Table 4-1 Replacement rules for missing reference start/end dates and TP start/end dates

	Choice	VPR regimens	Treatment group B
Reference start date	1 st	eCRF	Randomization date
	2 nd	a. If study drug exposure unknown, use randomization date b. If no study drug exposure (FAS not SAF) use SV last visit end date	
Reference end date / Last TP end date	1 st	eCRF	EoT visit start date

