- The second Analysis TP is assigned the next higher even TP number, starts with day 85 and ends with the last day reported in the original protocol TP, even if this exceeds a total of 168 days.

For example, protocol TP1 = analysis TP1 + analysis TP2. Protocol TP2 = analysis TP 3 + analysis TP 4 etc.

If the original planned protocol TP is less than 85 days, no such second evenly numbered Analysis TP will be assigned. As a result of this a subject in 6/2 regimen might have Analysis TP 1, TP 3 and TP 4, but no Analysis TP 2.

If the end date of the current treatment period is equal to the start date of the next treatment period based on CRF entries, it is assumed that the current treatment period ended one day earlier. The end date of the current treatment period is therefore moved back by one day.

For all TPs excluding the last TP, in case end of TP date is still missing, it will be replaced by the date of the last study drug intake within the respective TP according to diary (EXCATN=5 and EXMEDN>=1).

Subjects in treatment group B don't have any breaks. In the treatment group B TPs will be defined as consecutive 84-day time intervals starting with the date of randomization.

Replacement rules for missing end date of the last TP are analogue to those described for reference end dates.

TPs will be numbered sequentially.

Time intervals

Due to the complex visit schedule of the studies, a time-interval based approach is chosen to present data over time. Therefore, time intervals are defined which are used for different analysis topics.

The selection of time intervals used for a certain analysis topic will be described within each section.

An overview of the time intervals is given in [Figure 4-1](#).

Figure 4-1: Time interval overview

BL/Post baseline	Post baseline																										
Intervals A	Treatment Phase																		FUP Phase								
Intervals B	TP1 + BR1						TP2 + BR2						TPx						FUP1+2			FUP ...					
Intervals C	TP1			BR1			TP2			BR2			TPx			FUP1			FUP2			FUP ...					
Intervals D	BL	BL	BL	TP1	TP1	TP1	BR1	BR1	BR1	TP2	TP2	TP2	BR2	BR2	BR2	TPx	TPx	TPx	FUP	FUP	FUP	FUP	FUP	FUP	FUP	FUP	FUP
	1-28	29-56	57-x	1-28	29-56	57-84	1-28	29-56	...	1-28	29-56	57-84	1-28	29-56	...	1-28	29-56	57-84	1-28	29-56	57-84
AE Intervals	Pre-treatment			"on" (TP1 + 8d)			"off"			"on" (TP2 + 8d)			"off"			"on": TPx + 8d			"off"			Post-treatment (Start: day 61 after EoT)					

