6.5.3.5 AEs

All AEs will be coded by MedDRA terms (current version at time point of analysis) and classified into pre-treatment AEs, treatment-emergent (TEAE) and post-treatment AEs.

All AEs will be flagged as treatment-emergent adverse event (TEAE) except all AEs where there is clear evidence that the event starts before date of first study drug exposure (pre-treatment AEs) or after the date of last study drug exposure + 60 days (post-treatment AE). For Treatment group B, the reference start/end dates (as defined in section 4.5 Data Rules) will be used for this derivation, rather than date of first study drug exposure/ date of last study drug exposure. AEs with clear evidence of start before the date of first study drug exposure are flagged as pre-treatment AE unless the AE worsens at or after the date of first study drug exposure and before or at the date of last study drug exposure + 60 days. AEs starting before but worsening at or after the date of first study drug exposure and before or at the date of last study drug exposure + 60 days will be considered as two events, a pre-treatment AE and a TEAE. The pre-treatment AE will stop at the time of worsening and the new TEAE will start at the time of worsening. Same applies in case an AE starts at or after the date of first study drug administration, but before the date of last study drug administration + 60 days and worsens afterwards then e.g. leading to a TEAE and a post-treatment AE.

Reasons for worsening of an AE are listed below.

- AE intensity/grade is worsened (e.g.: moderate to severe)
- AE changed to a serious event
- AE ends with death
- AE is drug-related

TEAEs will further be categorized into on-treatment and off-treatment events.

All TEAEs should be flagged as on-treatment events except all TEAEs where there is clear evidence that the event starts outside all on-treatment phases. Each on-treatment phase starts with the date of first study drug exposure and ends with the date of last study drug exposure during a treatment period plus 8 days. For subjects in the VPR-6/2 treatment group, TEAEs with an onset within 8 days after end of TP1 (or TP3 or any TP with an odd number), but after start of TP2 (TP4 or after any TP with even number) will be reported as on-treatment for TP2 (TP4 and so on).

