6.5.3.11 Adrenal monitoring

Subjects were asked to undergo scheduled adrenal monitoring at the safety closeout visit. The adrenal monitoring comprises the following assessments:

- Adrenal gland imaging
- Laboratory testing
- Signs and symptoms suggestive of hypercortisolism, hyperaldosteronism

All tables generated within this adrenal monitoring section will contain the absolute number of subjects and percentage among subjects who performed the safety closeout visit.

An *overview* table will be provided. This table includes the number and percentage of subjects taking part at the specific adrenal monitoring assessments. The following numbers and percentages of subjects will be provided in addition:

- Subjects with abnormal result in at least one of the assessments.
- Subjects with abnormal result for each specific assessment separately.
- Subjects for whom an external expert recommendation was obtained. Among those, also the number and percentage of subjects with any findings suspicious of an adrenal disorder and recommendation for further handling will be provided.
- Subjects who have seen a local specialist (including information on type of specialist).

Details of the *final diagnosis by the expert panel* will be provided in another table. This table contains the number and percentage of subjects assessed by an expert, subjects needed expert panel meeting, subjects where expert panel met, and subjects with at least one diagnosis by the expert panel. Among those, the following numbers and percentages of subjects will be provided:

- Subjects with agreement of the diagnosis among all three experts.
- Subjects with a specific diagnosis (multiple diagnoses are possible).

A listing of subjects with other diagnosis (i.e. diagnosis entered by the expert panel in a text field) will be provided. A listing of subjects with adrenal tumor will be presented as well. It includes diagnosis, time from last study drug until date of panel assessment and possible causal relationship to study drug. Cases where the three experts did not agree on a diagnosis, are presented in a separate listing including also the diagnosis of the local specialist.

A third table will summarize the *diagnosis by a local specialist*. This table contains the number and percentage of subjects with at least one diagnosis by the local specialist. Among those, the numbers and percentages of subjects with a specific diagnosis (multiple diagnoses are possible) will be reported.

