6.5.3.12 Skin monitoring

Findings resulting from skin monitoring will be analyzed descriptively by treatment group. All subjects who consent for safety follow-up and attend the Safety closeout visit will undergo a thorough skin examination by a dermatology expert. The information will be recorded on the eCRF assigned to the safety closeout visit. The analysis will show the number of subjects who consented to participate in the Safety Follow-up, how many were assessed by a dermatologist or other clinician, which diagnostic tests were used and the results of the assessment as follows: number of

normal and abnormal findings; and following an abnormal finding which type of abnormality as recorded in the eCRF: 'Precancerous skin lesion', 'Cutaneous sarcoma', 'Other malignant skin tumor' and 'Other skin abnormality'.

Relevant cases will be reported as AEs, potentially as an AESI, and a narrative will be written.

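### Adrenal and skin findings first dated at the safety closeout fall outside the TEAE window for vilaprisan but can fall inside it for group B, so TEAE rows for these events can understate vilaprisan

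*SAP*

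**What the plan says.** **TEAE window (SAP 6.5.3.5 and Figure 4-1).** The default is inclusive: "All AEs will be flagged as treatment-emergent adverse event (TEAE) except all AEs where there is clear evidence" of onset outside the window. The upper limit is crossed when onset is clearly "after the date of last study drug exposure + 60 days (post-treatment AE". Figure 4-1 agrees: "Post-treatment (Start: day 61 after EoT". For group B, 6.5.3.5 uses the reference start and end dates in place of the exposure dates.

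**When adrenal and skin are examined.** Section 6.5.3.11: "Subjects were asked to undergo scheduled adrenal monitoring at the safety closeout visit". Section 6.5.3.12 places the skin examination at the same visit and adds: "Relevant cases will be reported as AEs, potentially as an AESI, and a narrative will be written". The adrenal section has no such sentence, but 6.5.3.5 lists both adrenal and skin disorders among the AESIs that investigators flag.

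**When treatment ended (Section 3).** Amendment 9 let vilaprisan subjects finish only the running 3-month course, or the running half of a 6-month course. From Amendment 10, "No subjects will receive further study drug treatment". For the control arm after Amendment 9, "Subjects in treatment group B can continue the study course following the current valid version of the protocol". Vilaprisan subjects who had already completed or discontinued were also asked back for the safety evaluation; in group B only those still in the study were asked.

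**Group B end date (Section 4.5, Table 4-1).** It is the EoT visit date. Otherwise, "Missing EoT visit dates will be replaced by the end date of the last available visit before the safety closeout visit".

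**The concern.** The closeout was added because of specific safety questions, adrenal and skin among them. A finding made there is placed in or out of the TEAE set by its distance from the end of treatment, and that distance differs by arm. Vilaprisan subjects reach the closeout long after their last tablet. Group B subjects are invited only if still in the study, and may reach it close to their reference end date. A TEAE row that compares the arms for adrenal or skin events could then show fewer events under vilaprisan because of visit timing alone. An exposure-adjusted TEAE rate would not cure this, because the events would already have left the numerator.

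**Working it through.** The SAP gives no figure on this point to reproduce. The check is date arithmetic, followed by an illustration on assumed rates.

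**Inputs from the SAP**
- Amendment 9: 11 Dec 2018; Amendment 10: 21 Nov 2019 (Section 1).
- Longest remaining dosing after Amendment 9: about 84 days (Section 3).
- TEAE window: 60 days after last exposure, or after the reference end date in group B (6.5.3.5).
- Follow-up after EoT: 24 or 12 weeks (Section 3).
- Vilaprisan recovery BMD scan, part of the monitoring before closure: at least 6 months after last intake (Section 3); a month is 30 days (6.5.1).

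**Vilaprisan**
1. Latest last tablet, with no implementation delay: 11 Dec 2018 + 84 days = 5 Mar 2019.
2. Window closes: 5 Mar 2019 + 60 days = 4 May 2019.
3. Last tablet to Amendment 10: 5 Mar to 21 Nov 2019 = 261 days. Past the window: 261 - 60 = 201 days.
4. Sensitivity: a closeout on the Amendment 10 date falls inside the window only if Amendment 9 took effect at a site 201 or more days late. The SAP gives no implementation dates. A later closeout needs a longer delay.
5. Cross-check: the recovery scan comes at 6 x 30 = 180 days or more, which is 180 - 60 = 120 days past the window.

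**Group B**
1. A closeout on 21 Nov 2019 is inside the window for any reference end date from 21 Nov - 60 days = 22 Sep 2019 onward.
2. A subject randomised on 11 Dec 2018 for about one year (365 days) would reach EoT about 11 Dec 2019, after Amendment 10. Closeouts within 60 days of EoT are therefore possible.
3. They are not certain. Planned follow-up runs to 84 or 168 days after EoT, and a subject seen beyond day 60 is outside the window too.

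**Illustration (all rates assumed).** Let *p* be the share of closeout attendees with a new finding, equal in both arms; *f* the share of group B closeouts inside the window; *u* the share of findings without clear evidence of late onset, which stay TEAEs in either arm. All vilaprisan closeouts are taken to be outside the window.
- Vilaprisan TEAE share = p x u
- Group B TEAE share = p x [f + (1 - f) x u]
- Difference, vilaprisan minus B = -p x f x (1 - u)

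With p = 5%, in percentage points:

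| u | f = 10% | f = 50% | f = 100% |
|---|---|---|---|
| 0 | -0.5 | -2.5 | -5.0 |
| 50% | -0.25 | -1.25 | -2.5 |
| 100% | 0 | 0 | 0 |

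At u = 0 and f = 50%, p = 2% gives -1.0 and p = 10% gives -5.0. These are shares of attendees. A table on the full safety set would also depend on how many subjects in each arm attended, which the SAP does not give.

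**The case against.** The strongest counter-argument is the default in 6.5.3.5. A first adrenal image or skin examination shows when a lesion was found, not when it began. If onset is left unclear, the event stays a TEAE in both arms and the difference among attendees is zero, as the last row of the table shows. This stands, and it rules out the inference that vilaprisan findings are excluded by construction. It does not close the point: the SAP does not say how onset is dated for findings first seen at closeout, and an entered detection date may be read as clear evidence.

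Other limits also stand:
- **AESI tables.** A reader might infer that these are biased too. Section 6.5.3.5 does not restrict them to TEAEs. It does not say that post-treatment events are included either, whereas the ovarian-cyst AE analysis in 6.5.3.4 names all three phases.
- **Dedicated tables.** Sections 6.5.3.11 and 6.5.3.12 report adrenal and skin results without the 60-day limit. The adrenal tables use closeout attendees as denominator, and the adrenal-tumour listing shows time from last study drug to panel assessment. The findings are not hidden.
- **Every vilaprisan subject.** This is inferred from protocol version dates and is not stated. Under Section 4.5 and Table 4-1, a subject with unknown exposure, or with no end date in eCRF or diary, takes a last visit as reference end date, which may be the closeout itself.
- **Endometrium.** Section 6.5.2.1 analyses histology by treatment period as well as at exit, so the argument does not carry over.
- **No formal test.** The SAP plans no test or decision rule on TEAEs, and the primary safety variable is lumbar spine BMD.

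These points limit the harm. They do not make TEAE rows for adrenal and skin events comparable between arms, and nothing in the SAP warns the reader of that.

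**Conclusion.** The point holds in limited form. For essentially all vilaprisan subjects with a known last dose, the closeout lies well past the TEAE window: at least 201 days, if Amendment 9 took effect on its date and at most 84 days of dosing remained. For group B it can lie inside the window. TEAE rows for adrenal and skin events can therefore understate vilaprisan relative to group B, provided that detection dates are recorded as onset dates.

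The size is unknown. It depends on the finding rate, the share of group B closeouts within 60 days of the reference end date, and how onset is recorded; the SAP gives none of these. The illustration runs from 0 to -5.0 percentage points at an assumed 5% finding rate. A reader might go further and conclude that vilaprisan must show 0% or that the AESI comparison fails. The SAP does not support either, for the reasons given above.

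That the SAP shows these work-ups only at closeout is read from the SAP alone; the protocol was not available. Should-fix, not must-fix.

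**What to change.** In SAP 6.5.3.5, for the adrenal and skin AESI groups, both investigator-based and MedDRA-based:
1. Present all events from the reference start date through the closeout visit, without the 60-day cut.
2. Split them into events reported before closeout and events first detected at the closeout work-up. Use closeout attendees as denominator for the second part, since the two arms were invited on different terms.
3. Show time since last dose (for group B, since the reference end date).
4. State that TEAE-only rows for these groups are not used to compare vilaprisan with group B.
5. Add one sentence on whether a detection date at closeout counts as clear evidence of onset for the TEAE flag.

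The cost is SAP wording and one or two extra tables on data already planned for collection. The drawback is that events long after treatment enter the table, which is why time since last dose must be shown beside them.

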6.5.3.6 Laboratory parameters

For immunology and coagulation parameters Intervals ‘BL/Post baseline’ will be used, while for all other laboratory measurements the following time intervals will be considered:

- Intervals C (according to Figure 4-1)

The tabulation will follow in principle the Bayer Global Standard Tables catalogue (currently V 4.0 default), with the necessary modifications like for time interval presentation instead of visit presentation.

The maximum or minimum measurement within the time interval will be used for calculations, following a worst-case approach (for details please refer to Appendix 2). Scheduled as well as unscheduled measurements will be considered.

Central as well as local lab measurements are available. Summary statistics will be provided based on central lab. Local lab measurements will be listed.

Values below the lower limit of quantification (LLOQ) will be set to LLOQ/2.

Values above the upper limit of quantification (ULOQ) will be set to ULOQ.

6.5.3.7 Estradiol

Absolute values will be analyzed using descriptive statistics by treatment group using time intervals C and D. The lowest value (i.e. “worst case”) per subject per time interval will be used in the analyses.

The distribution of estradiol values by treatment group using time intervals C and D like above will be graphically depicted with boxplots. The time course will be shown using line plots depicting the mean and 95% confidence interval (two-sided) and using time intervals C and D as described above. Time intervals including data from less than 10 of randomized subjects in the respective group will be excluded from plots.

For estradiol frequency tables with number and percentage of subjects with estradiol (pg/mL) <13, <30 will be displayed by treatment group and time intervals A and B. For each time interval, the subjects with at least one lower value based on each cut-off in any visit during that time interval will be counted.

